## List of Abbreviations

5-HVLX-gluc	5-hydroxyviloxazine glucuronide
ADR	adverse drug reaction
AE	adverse event
Am milk	total amount of drug excreted in breast milk
ATC-4	Anatomical Therapeutic Chemical Level 4
AUC	area under the concentration-time curve
AUC tau,milk	area under the concentration-time curve over a 24-hour dosing interval in breast milk
AUC tau,ss	area under the concentration-time curve over a 24-hour dosing interval in plasma at steady-state
BLQ	below the limit of quantification
BMI	body mass index
C ave,milk	average concentration in breast milk
C ave,ss	average concentration in plasma at steady-state
CL/F ss	apparent total body clearance in plasma at steady-state
C max,milk	maximum observed concentration in breast milk
C max,ss	maximum observed concentration in plasma at steady-state
C trough,milk	drug trough concentration immediately before the next dose in breast milk
C trough,ss	drug trough concentration immediately before the next dose in plasma at steady-state
C-SSRS	Columbia Suicide Severity Rating Scale
CV	coefficient of variation
DID	daily infant dosage
EDID	estimated daily infant dosage
ECG	electrocardiogram
eCRF	electronic case report form
EOS	end of study
HR	heart rate
MedDRA	Medical Dictionary for Regulatory Activities
ML/PL	breast milk-plasma ratio
NCA	non-compartmental analysis
PK	pharmacokinetic
PN	preferred name
PT	preferred term
Q1	first quartile

Q3	third quartile
QD	once daily
QTcF	QT interval corrected for heart rate using Fridericia's formula
RID	relative infant dose
SADR	suspected adverse drug reaction
SAE	serious adverse event
SAP	statistical analysis plan
SD	standard deviation
SM	study medication
SOC	system organ class
$t_{1/2}$	apparent terminal elimination half-life
TEAE	treatment-emergent adverse event
$T_{max,milk}$	time of maximum observed concentration in breast milk
$T_{max,ss}$	time of maximum observed concentration in plasma at steady-state
WHODrug	World Health Organization Drug Dictionary

## 1. Introduction

SPN-812 (viloxazine extended-release capsules; QELBREE®) is a structurally distinct, bicyclic, norepinephrine reuptake inhibitor. The active substance in SPN-812 is viloxazine, whose mechanism of action is multimodal with antagonistic activity observed at 5-HT2B and agonistic activity at 5-HT2C receptors, as well as weaker antagonistic effects at ADR $\alpha$ 1B, ADR $\beta$ 2 and 5-HT7 receptors. Additionally, SPN-812 acts as a modulator with inhibitory effects at the norepinephrine reuptake transporter. Viloxazine was previously marketed in several European countries as an antidepressant as an immediate-release product. An extended-release formulation of viloxazine, SPN-812, has been developed by Supernus to prolong the release and absorption of viroxazine post-administration, thereby allowing longer dosing intervals for a drug with a relatively short half-life. As of April 2022, SPN-812 ([QELBREE® PI](#)) is Food and Drug Administration-approved for the treatment of Attention-Deficit Hyperactivity Disorder in persons 6 years of age and older.

This is an open label, single treatment, lactation study of SPN-812 in healthy lactating women. The study is designed to assess the excretion of viroxazine and its major metabolite 5-hydroxyviroxazine glucuronide (5-HVLX-gluc) into breast milk following repeated administration of SPN-812 600 mg, once daily (QD).

The purpose of this statistical analysis plan (SAP) is to define the planned statistical analysis of the study data consistent with the study objectives. This SAP is written based on protocol 812P418, version 2.0, dated 02 September 2022.

## 2. Objectives and Endpoints

### 2.1 Primary Objective and Endpoints

The primary objective is to:

- Evaluate the pharmacokinetics (PK) of viroxazine and its major metabolite 5-hydroxyviroxazine glucuronide (5-HVLX-gluc) in breast milk in healthy lactating women following multiple oral doses of SPN-812.

The primary endpoints of this study are as below:

- Breast milk PK parameters for viroxazine and 5-HVLX-gluc when SPN-812 reaches plasma steady-state:
  - Area under the concentration-time curve (AUC) over a 24 hour dosing interval in breast milk ( $AUC_{\text{tau,milk}}$ )
  - Maximum observed concentration in breast milk ( $C_{\text{max,milk}}$ )
  - Time of maximum observed concentration in breast milk ( $T_{\text{max,milk}}$ )
  - Drug trough concentration immediately before the next dose in breast milk ( $C_{\text{trough,milk}}$ )

- Average drug concentration in breast milk ( $C_{ave,milk}$ )
- Total amount of drug excreted in breast milk ( $A_{milk}$ , mg/day) over a period of 24 hours

## 2.2 Secondary Objectives and Endpoints

The secondary objectives are to:

- Evaluate the PK of viloxazine and 5-HVLX-gluc in plasma in healthy lactating women following multiple oral doses of SPN-812.
- Evaluate the overall exposure between breast milk and plasma in healthy lactating women following multiple oral doses of SPN-812.
- Estimate daily infant dose of SPN-812 via breast milk.

The secondary endpoints of this study are as below:

- Plasma PK parameters for viloxazine and 5-HVLX-gluc at plasma steady-state, if applicable:
  - AUC over a 24 hour dosing interval in plasma at steady-state ( $AUC_{tau,ss}$ )
  - Maximum observed concentration in plasma at steady-state ( $C_{max,ss}$ )
  - Time of maximum observed concentration in plasma at steady-state ( $T_{max,ss}$ )
  - Apparent total body clearance in plasma at steady-state ( $CL/F_{ss}$ )
  - Average concentration in plasma at steady-state ( $C_{ave,ss}$ )
  - Drug trough concentration immediately before the next dose in plasma at steady-state ( $C_{trough,ss}$ )
- Breast milk-plasma ratio (ML/PL) based on AUC over 24 hours for viloxazine and 5-HVLX-gluc at plasma steady-state
- Estimated daily infant dosage (EDID, mg/kg/day) and relative infant dose (RID, %) at plasma steady-state

## 2.3 Safety Objective and Endpoints

The safety objective is to:

- Evaluate the safety and tolerability of multiple doses of SPN-812 in healthy lactating women.

The safety endpoints of this study are as below:

- Adverse events (AEs)
- Clinical laboratory test results (clinical chemistry, hematology, and urinalysis)
- 12-lead electrocardiogram (ECG)
- Columbia Suicide Severity Rating Scale (C-SSRS)
- Vital signs
- Physical examination
- Concomitant medications

### 3. Study Design

[figure not shown]
This is an open label, single treatment, lactation study of SPN-812 in healthy lactating women. The study is designed to assess the excretion of viloxazine and its major metabolite 5-HVLX-gluc into breast milk following repeated administration of SPN-812 600 mg, once daily (QD).

This study is comprised of Screening, Inpatient Admission, Treatment Period, and End of Study (EOS). The total duration of the study is up to around 1 month including Screening up to 28 days and 4 days of Treatment Period. Subjects will remain in the inpatient unit for 5 days, including the day of admission to the inpatient unit (Day -1), 3 days of dosing study medication (SM) (Days 1-3), and the day of discharge (Day 4).

Subjects will be screened within 28 days prior to dosing. After informed consent is obtained, information from subjects will be collected (including maternal-related information) and subjects will undergo screening evaluations (see [Table 13-1](#)). Inclusion/exclusion criteria will be reviewed to determine the subjects' eligibility at Screening. A lactation consultant will be available to provide lactation support to subjects once they are enrolled.

Subjects will be admitted to inpatient unit on Day -1 to confirm eligibility. Subjects will receive 600 mg SPN-812 on the morning of Days 1, 2, and 3 after completion of safety assessments. Study medication should be administered at the same time in the morning ( $\pm 30$  min) of dosing days. Breast milk and blood sample for PK analysis will then be collected on Day 3 to 4 per schedule in [Section 8.2](#) and [Section 8.3](#), respectively. Non-PK breast milk expressed on Days -1, 1, and 2 will be collected over the time intervals in [Section 8.2](#), and these samples will not be analyzed for drug concentrations. The volume and the start and end times of the collection of each non-PK and PK breast milk sample will be recorded. The EOS procedures will be conducted prior to discharge on Day 4 following the last breast milk and blood sample collection. If subject discontinues early, all EOS procedures will be conducted. Study schematic is shown in [Figure 3-1](#) and Schedule of Events and Procedures is presented in [Table 13-1](#).

**Figure 3-1: Study Schematic**

#### 4. General Statistical Considerations

All statistical analyses will be conducted using statistical analysis system SAS® Version 9.4 or higher (SAS Institute, Cary, NC).

Descriptive statistics for continuous variables will include number of subjects, mean, standard deviation (SD), median, first quartile (Q1), third quartile (Q3), minimum, and maximum, unless otherwise noted. For categorical variables, frequencies and percentages will be presented.

All tables, listings, and figures will be presented with treatment. The treatment below will be used for presentations:

- SPN-812 600 mg QD

All data listings will be sorted by subject number.

No algorithm for imputation of missing data will be employed.

Study days are calculated with respect to the first dose date as below:

- If the assessment/observation date is on or after the first dose date, then Study Day = Assessment/Observation Date – First Dose Date + 1
- Otherwise, Study Day = Assessment/Observation Date – First Dose Date

Baseline will be defined as the last non-missing assessment (including repeated and unscheduled assessments) before the first dose of SM administration, unless otherwise specified.

For summary of safety assessments, if there are repeated measurements at a time point, the first non-missing assessment at that time point will be used in the summary tables.

Unscheduled results will not be included in the summary tables, except for determining Baseline, but will be presented in data listings.

The methodology and data handling specifications for PK data are detailed in [Section 8](#).

#### **4.1. Sample Size**

The sample size is not based on statistical power considerations. Based on clinical judgement, up to 15 healthy lactating volunteers will be enrolled in the study, with the expectation that at least 12 subjects will complete the study.

#### **4.2. Randomization, Stratification, and Blinding**

This is an open label, single treatment study, no randomization, stratification, and blinding will be used.

#### **4.3. Analysis Population**

The Enrolled Population will include all subjects who sign the informed consent form.

The Safety Population will include all subjects who receive at least one dose of SM.

The PK Population will include all subjects in the Safety Population who have a sufficient PK profile to derive at least 1 PK parameter without major events that could impact the PK data (e.g., emesis).

For subjects experiencing emesis following the administration of SPN-812, PK parameters will be determined and listed, however, parameters for these subjects may be excluded from the affected statistical analysis (i.e., descriptive statistics) per the study pharmacokineticist's discretion.

Subjects experiencing emesis before study Day 3 may be invited to continue participation in the study if deemed appropriate by the Principal/Site Investigator. The accurate time of emesis should be recorded.

### **5. Subject Disposition**

#### **5.1 Disposition**

The following will be summarized for the Enrolled Population for all subjects:

- The number of subjects who completed screening
- The number of subjects who did not complete screening
  - Reasons for discontinuation from screening
- The number of subjects who completed study

- The number of subjects who did not complete study
  - Reasons for discontinuation from the study
- The number of subjects in each analysis population

Subject disposition data will be presented in data listings.

## 5.2 Protocol Deviations

A protocol deviation is any change, divergence, or departure from the study design or procedures defined in the protocol. An important deviation (sometimes referred to as a major or significant deviation) is a subset of protocol deviations that significantly affects the subject's rights, safety, or well-being and/or the completeness, accuracy, and reliability of the study data, and may affect the conclusion of the safety and PK analyses. Important protocol deviations will be summarized for the Safety Population. All protocol deviations will be presented in a data listing.

## 5.3 Inclusion and Exclusion Criteria

Inclusion and exclusion criteria deviations will be presented in a data listing.

# 6. Demographics and Baseline Characteristics

## 6.1 Demographics

Demographic information collected at Screening will be presented in a data listing.

Descriptive statistics will be calculated for the following continuous demographic characteristics:

- Age (years)
- Weight (kg)
- Height (cm)
- Body mass index (BMI) (kg/m^2)

Frequency counts and percentages will be tabulated for the categorical variables:

- Sex
- Race
- Ethnicity

The summaries will be presented for the Safety Population.

## 6.2 Medical, Psychiatric, and Maternal History

The medical and psychiatric history data will be coded using the Medical Dictionary for Regulatory Activities (MedDRA, version 26.0) and presented in a data listing.

Edinburgh Postnatal Depression Scale and maternal (infant gestational age at delivery, stage of lactation, length of time postpartum, and feeding method [pumping or breastfeeding]) history will be presented in separate data listings.

## **7. Treatments and Medications**

### **7.1 Prior and Concomitant Medications**

Medications that stop prior to the first dose of SM will be classified as prior medication. Medications that start on or after the first dose of SM will be classified as concomitant. If a medication starts before the first dose of SM and stops on or after the first dose of SM, then the medication will be classified as both prior and concomitant.

Prior and concomitant medications will be summarized by Anatomical Therapeutic Chemical Level 4 (ATC-4) and preferred name (PN) for the Safety Population. All prior and concomitant medications will be coded according to the World Health Organization Drug Dictionary (WHODrug, version March 2023) and presented in a data listing.

### **7.2 Study Medication**

The SM administration and drug accountability data (including treatment received, date and time of dose, and dose level administered) as collected on electronic case report form (eCRF) will be presented in a data listing.

## **8. Pharmacokinetics**

All PK listings and individual concentration-time profiles will be presented using the Safety Population. The PK tables and mean figures will be presented using the PK Population.

### **8.1 Data Analyses**

Data rounding specifications for PK data are documented in the PK tables, listings, and figures shells.

For presentation of the individual data and summary statistics, viloxazine and 5-HVLX-gluc breast milk and plasma concentrations below the limit of quantitation (BLQ) will be set to zero. For the PK analysis (non-compartmental analysis [NCA]), concentrations BLQ up to the time of the first quantifiable concentration will be treated as zero. Embedded (values between 2 quantifiable concentrations) and terminal BLQ concentrations will be treated as “missing”.

Descriptive statistics (number of observations [n], number of BLQ values [nBLQ], mean, SD, coefficient of variation [CV], minimum, median, and maximum) will be used to summarize breast milk and plasma concentration data at each planned sampling time point for each analyte. The midpoint of the breast milk collection interval will be used as the breast milk sampling time.

A listing of the actual sampling times and corresponding concentrations will be provided for all PK samples. Individual breast milk volumes collected at each time interval as indicated in section 8.2 for both PK and non-PK samples will also be presented in breast milk data listing. Viloxazine and 5-HVLX-gluc mean breast milk and plasma concentration versus time profiles will be presented by using the scheduled sampling time on both linear and semi-logarithmic scales. Individual breast milk and plasma concentrations by actual sampling time will be provided on both linear and semi-logarithmic scales.

## 8.2 Breast Milk Collections

A total of 9 expressed PK breast milk samples will be collected for PK analysis at the following time intervals:

- Day 1: -4 to <0 hours pre-dose;
- Day 3: -4 to <0 hours pre-dose, and '0 to 4', '4 to 6', '6 to 8', '8 to 10', '10 to 12', '12 to 16', and '16 to 24' hours post-dose.

Non-PK breast milk expressed on Days -1, 1, and 2 will be collected over the time intervals as below, and these samples will not be analyzed for drug concentrations:

- Day -1: store milk as pumped per subject's pumping routine;
- Day 1: 0 to 24 hours post-dose per subject's pumping routine;
- Day 2: 0 to 20 hours post-dose per subject's pumping routine.

For each breast milk collection period, the start and end times of the collection will be recorded, and the total volume (mL) of breast milk collected will be measured and recorded.

## 8.3 Plasma Collections

A total of 13 blood draws for PK will be collected on Day 1 pre-dose, Day 3 pre-dose, and Day 3 at 0.5, 1.0, 2.0, 3.0, 4.0, 5.0, 6.0, 8.0, 10.0, 16.0, and 24.0 hours post-dose. The following windows are permitted relative to the specified PK sample collection times:

- Pre-dose: - 15 minutes;
- < 1 hour post-dose:  $\pm$  3 minutes;
- 1 to 8 hours post-dose:  $\pm$  5 minutes;
- 8 to 24 hours post-dose:  $\pm$  10 minutes.

The actual time and date of each blood sample collection will be recorded. Pharmacokinetic collections that have an actual sampling time that deviates from the predefined collection time windows will be flagged in the data listings.

## 8.4 Pharmacokinetic Parameters

Viloxazine and 5-HVLX-gluc breast milk and plasma concentration-time data will be analyzed by NCA using Phoenix® WinNonlin® Version 8.3.4 or higher (Certara USA, Inc., Princeton, NJ). The following PK parameters will be calculated for viloxazine and 5-HVLX-gluc, where data permits:

### Breast milk:

PK Parameter	Definition
$C_{max,milk}$	Maximum observed concentration in breast milk.
$C_{ave,milk}$	Average drug concentration in breast milk calculated as the ratio of $AUC_{tau,milk}/24$ .
$C_{trough,milk}$	Drug trough concentration immediately before the next dose in breast milk.
$T_{max,milk}$	Time of maximum observed concentration in breast milk.
$AUC_{tau,milk}$	Area under the concentration-time curve over a 24 hour dosing interval in breast milk, calculated using the linear up/log down rule.
$Am_{milk}$	Total amount of drug excreted in breast milk, calculated as the sum of the product of breast milk volumes and concentrations from each time period.
ML/PL	Breast milk-plasma ratio, calculated as $AUC_{tau,milk}/AUC_{tau,ss}$ .
DID	Daily infant dosage (mg/day); total drug present in breast milk and consumed by the infant per day, which is equal to $Am_{milk}$ .
EDID	Estimated daily infant dosage (mg/kg/day) calculated as $ML/PL \times$ the average maternal concentration in plasma ( $C_{ave,ss}$ ) $\times 150$ mL/kg/day (EDID 150) and 200 mL/kg/day (EDID 200), respectively
RID	Relative infant dose (%); the percent of the weight-adjusted maternal dosage consumed in breast milk over 24 hours, calculated as $EDID$ (mg/kg/day)/maternal dosage (mg/kg/day) $\times 100\%$ .

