7.2.3 Pharmacokinetic Parameters

[Table 2](#) shows the PK parameters that will be calculated based on plasma and milk concentration-time data using standard non-compartmental methods:

Table 2. Pharmacokinetic Parameter for Plasma/Breast Milk

Plasma PK Parameter At Plasma Steady-state	Parameter Description
AUC _{tau,ss}	Area under the plasma concentration-time curve over a 24 h dosing interval.
C _{ave,ss}	Average plasma concentration, calculated as the ratio of AUC _{tau,ss} /24.
C _{max,ss}	Maximum observed plasma concentration.
C _{trough,ss}	Observed plasma concentration immediately before the next dose.
CL _{ss} /F*	Apparent clearance.
T _{max,ss}	Time of the maximum measured plasma concentration. If the maximum value occurs at more than one time point, T _{max} is defined as the first time point with this value.
Breast Milk PK Parameter	Parameter Description
AUC _{tau,milk}	Area under the milk concentration-time curve over a 24-hour dosing interval.
Am _{milk}	Total amount of drug excreted in milk, calculated as the sum of the product of milk volumes and concentrations from each time period.
C _{ave,milk}	Average drug concentration in milk, calculated as the ratio of AUC _{tau,milk} /24.
C _{max,milk}	Maximum observed drug concentration in milk.
C _{trough,milk}	Observed drug concentration in milk immediately before the next dose
ML/PL	Milk-plasma ratio, calculated as AUC _{tau,milk} / AUC _{tau,ss} .
T _{max,milk}	Time of the maximum measured concentration in breast milk. If the maximum value occurs at more than one time point, T _{max} is defined as the first time point with this value.
DID	Daily infant dosage (mg/day); total drug present in milk and consumed by the infant per day, which is equal to Am _{milk} .
EDID	Estimated daily infant dosage (mg/kg/day) calculated as ML/PL x the average maternal plasma concentration (C _{ave,ss}) multiplied by 150 mL/kg/day and 200 mL/kg/day, respectively.
RID	Relative infant dose (%); the percent of the weight-adjusted maternal dosage consumed in breast milk over 24 hours, calculated as EDID (mg/kg/day)/maternal dosage (mg/kg/day) multiplied by 100 %.

*not calculated for 5-HVXL-gluc

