8.1.3.2 Pharmacokinetic Parameters

Viloxazine and 5-HVLX-gluc PK parameters (see [Section 7.2.3](#)) will be calculated from breast milk and plasma concentration-time data by standard non-compartmental methods using Phoenix™ WinNonlin® (Version 8.0 or higher, Certara) and will be summarized using descriptive statistics. All individual subject parameter data will be listed. A list of PK parameters for plasma and breast milk are presented in Table 2.

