### Plasma:

PK Parameter	Definition
$C_{max,ss}$	Maximum observed concentration in plasma at steady-state.
$C_{ave,ss}$	Average concentration in plasma at steady-state calculated as the ratio of $AUC_{tau,ss}/24$ .
$C_{trough,ss}$	Drug trough concentration immediately before the next dose in plasma at steady-state.

PK Parameter	Definition
$T_{max,ss}$	Time of maximum observed concentration in plasma at steady-state.
$AUC_{tau,ss}$	Area under the concentration-time curve over a 24 hour dosing interval in plasma at steady-state, calculated using the linear up/log down rule.
$CL/F_{ss}^*$	Apparent total body clearance in plasma at steady-state, calculated as: Dose/ $AUC_{tau,ss}$ .

\*not calculated for 5-HVLX-gluc

Actual sampling times and actual midpoint times will be used for the estimation of all PK parameters in breast milk and plasma, respectively.

Analysis: Viloxazine and 5-HVLX-gluc breast milk and plasma PK parameters will be presented in data listings and summarized by analyte using descriptive statistics (n, mean, SD, CV, minimum, median, maximum, geometric mean, and geometric CV).  $T_{max}$  will be summarized using n, median, minimum, and maximum only.

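### RID for 5-HVLX-gluc divides metabolite mass by parent-drug dose with no molecular-weight conversion, so unless the assay reports viloxazine equivalents it overstates the percent of maternal dosage by a constant factor

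*SAP*

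**What the plan says.** SAP 8.4 opens its parameter tables with: "The following PK parameters will be calculated for viloxazine and 5-HVLX-gluc, where data permits". RID is in the breast milk table, defined as "Relative infant dose (%); the percent of the weight-adjusted maternal dosage consumed in breast milk over 24 hours". The results are then reported for each analyte: "Viloxazine and 5-HVLX-gluc breast milk and plasma PK parameters will be presented in data listings and summarized by analyte using descriptive statistics". The SAP has one metabolite exemption, the footnote to CL/F: "not calculated for 5-HVLX-gluc".

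The protocol has the same structure. Section 8.1.3.2 has PK parameters computed for both analytes and adds: "A list of PK parameters for plasma and breast milk are presented in Table 2". Table 2 in Section 7.2.3 gives RID as "calculated as EDID (mg/kg/day)/maternal dosage (mg/kg/day) multiplied by 100", and its only metabolite footnote ("not calculated for 5-HVXL-gluc") again attaches to CL/F. EDID, the numerator of RID, is the milk-plasma ratio times average maternal plasma concentration, "multiplied by 150 mL/kg/day and 200 mL/kg/day, respectively".

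Protocol 5.1 expresses capsule strength as mass of viloxazine free base. Protocol 7.2.2 says that viloxazine and 5-HVLX-gluc concentrations will be measured by validated tandem mass spectrometry, without stating a reporting basis. Neither document mentions molar units, viloxazine equivalents or a molecular-weight factor.

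**The concern.** A percent of the maternal dosage needs the same substance, or the same molar basis, above and below the line. For viloxazine this holds. For the metabolite, the denominator is mg of viloxazine free base, while the numerator is, on the natural reading of Protocol 7.2.2, mg of 5-HVLX-gluc. Each mole of viloxazine that becomes the glucuronide gains the mass of an oxygen and a glucuronic acid residue, none of which was part of the dose. The result is a mass ratio of two different molecules under a label that says percent of maternal dosage.

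Only two listed parameters set the maternal dose against an analyte quantity: CL/F (dose over AUC) and RID (EDID over dosage). The metabolite is exempted from CL/F but not from RID. ML/PL compares an analyte with itself, and EDID, DID and Am_milk do not involve the dose.

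At stake are the mean, median and geometric mean of metabolite RID, at both intake volumes. These are the figures a reader would quote.

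**Working it through.** The plan states no figure for this quantity, so there is nothing to reproduce. The check is algebra on the plan's definitions, then a range for the factor.

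**Inputs from the documents**
- EDID = ML/PL × C_ave,ss × V, with V = 150 or 200 mL/kg/day (SAP 8.4; Protocol Table 2).
- ML/PL = AUC_tau,milk / AUC_tau,ss, and both average concentrations are AUC/24, so EDID = C_ave,milk × V.
- RID = EDID / maternal dosage × 100.
- Maternal dosage = 600 mg per day over body weight, as viloxazine free base (Protocol 5.1, 5.2).

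**Assumption.** The documents give no molecular weights. Hydroxylation is taken to add 15.999 g/mol and glucuronidation 176.12 g/mol, together 192.12 g/mol. The parent weight M is left open between 150 and 400 g/mol.

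**Overstatement if the assay reports mass of glucuronide**

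RID in viloxazine equivalents = RID as written × M / (M + 192.12), so

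RID as written / RID in equivalents = (M + 192.12) / M = 1 + 192.12/M.

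| Assumed M (g/mol) | As written / in equivalents | In equivalents / as written |
|---|---|---|
| 150 | 2.28 | 0.44 |
| 200 | 1.96 | 0.51 |
| 300 | 1.64 | 0.61 |
| 400 | 1.48 | 0.68 |

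Concentration, body weight, ML/PL and V all cancel. The factor exceeds 1 for any parent weight.

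**Illustration with assumed values.** Take metabolite C_ave,milk = 0.5 µg/mL, maternal weight 70 kg and M = 300.
- Maternal dosage = 600/70 = 8.571 mg/kg/day.
- At 150 mL/kg/day: EDID = 0.075 mg/kg/day; RID as written = 0.075/8.571 × 100 = 0.875%; in equivalents = 0.875/1.640 = 0.53%.
- At 200 mL/kg/day: EDID = 0.100 mg/kg/day; RID as written = 1.167%; in equivalents = 1.167/1.640 = 0.71%.

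The ratio is the same at both intakes. The absolute values only illustrate the arithmetic; the documents contain no metabolite milk concentration.

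**Scale.** Moving from 150 to 200 mL/kg/day changes RID by 200/150 = 1.33. The mass factor equals 1.33 when 192.12/M = 1/3, that is M = 576 g/mol, and is larger for any lighter parent.

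**The opposite error.** If results are already in viloxazine equivalents and someone still applies the conversion, RID falls to M/(M + 192.12) of its true value: 0.44 to 0.68 over the same range.

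**The case against.** The strongest reply is that no error has been shown. The deciding fact, the reporting basis of the assay, belongs to the bioanalytical method, whose reports will be appended to the study report (Protocol 10.4.4). If results are in viloxazine equivalents, the plan is correct. This stands as a condition on the finding. It does not remove it, because the natural reading is concentrations of the glucuronide itself, and on that reading the formula does not yield the labelled quantity. Silence also leaves room for error in either direction.

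It can also be said that metabolite RID may never have been intended. The plasma and ML/PL endpoint bullets name both analytes; the EDID/RID bullet names neither, and the matching objective speaks of the infant dose of SPN-812. The plasma bullet lists CL/F for both analytes, if applicable, although the tables exempt the metabolite, so generic wording is weak evidence of intent. This too stands: metabolite RID is not clearly a designated secondary endpoint. It is nevertheless a planned calculation, tabulated by analyte, and the protocol's EDID/RID bullet points to Table 2, where only CL/F is exempted.

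Finally, the consequence is modest. The factor is one constant that a reader could apply later. It leaves CV, geometric CV and ranking unchanged, and it overstates infant exposure. No RID threshold is set, and no sum of parent and metabolite RID is planned. The 150 and 200 mL/kg/day intakes are reporting scenarios, not an error tolerance, so 1.33 is a yardstick only. All of this limits the weight of the point; none of it makes the label correct.

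**Conclusion.** The concern holds, conditionally. If 5-HVLX-gluc concentrations are reported as mass of glucuronide, metabolite RID overstates the percent of maternal dosage by (M + 192)/M: between 1.48 and 2.28 for an assumed parent weight of 400 down to 150 g/mol. The size rests on the assumed added mass and parent weight; the upward direction needs only that the metabolite is heavier per mole than the parent. If results are in viloxazine equivalents, there is no overstatement and the gap is the missing statement of basis.

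The effect is confined to the two metabolite RIDs, from EDID 150 and EDID 200. Viloxazine RID, the primary endpoints, and metabolite EDID, DID, Am_milk and ML/PL are not touched. It should be corrected before the tables are produced, but it does not threaten the study's main conclusions. Confidence is medium, because the reporting basis is not in the documents.

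**What to change.** Ask the bioanalytical laboratory for the reporting basis of 5-HVLX-gluc, then amend SAP 8.4 in one of two ways.

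1. Keep metabolite RID and state the basis. If it is mass of glucuronide, define metabolite RID as EDID × (MW viloxazine / MW 5-HVLX-gluc) / maternal dosage × 100 and give both molecular weights. If it is already viloxazine equivalents, say so and apply no conversion.
2. Drop metabolite RID by extending the existing CL/F footnote to RID.

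In either case, name the analyte or analytes in the EDID/RID endpoint bullet so that it agrees with the table.

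The cost is one query to the laboratory and one constant or footnote in the SAP. Aligning Protocol Table 2 needs a sponsor-approved amendment or administrative change (Protocol 10.2) and can wait for the next one. No new samples or data are needed.
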